1.2 RATIONALE FOR RESEARCH PROJECT

This research is needed to tackle the compound pressures that have led to 7.3 million people waiting for consultant-led elective care. Waits for 3.3 million people are over 18 weeks and 360,000 are waiting for over one year. 13 These waits impact health and wellbeing and increase the pressure

NIHR 158681BADGER			
Protocol Version 2.0 18/06/2024	CPMS: 58336	IRAS No: 333799	CPRD ID: 24_004022

across the health and social care system.¹⁴ The National Elective Care Recovery and Transformation Programme⁴ seeks to eliminate waits of longer than a year for elective care by March 2025. One of the key components identified to support delivery is the mobilisation of A&G services.

Efficient and timely communication using A&G has great potential to reduce compound pressures by shortening patient journeys through the system, enabling prompt appropriate management of conditions requiring specialist advice, and reducing the burden on primary care that is exacerbated by long waits for specialist opinions. The Transformation Programme⁴ has identified A&G as reducing the need for people to travel for hours to a hospital appointment lasting a few minutes saving time, cost, and stress by doing things differently as well as having a positive environmental impact. This in turn supports the Government aim to Deliver a Net Zero National Health Service¹⁵ and can also address health inequalities as access to specialist advice is delivered locally by primary care teams through effective joint working across services.

The COVID pandemic accelerated use of the A&G process, which has been in use since 2012. There were approximately 135,000 A&G referrals sent through e-RS in February 2023.8 However, there are misgivings amongst those who use A&G, with GPs expressing concerns over increasing workload, the potential for A&G to 'block' necessary referrals, and a requirement for practitioners to work beyond their competence. Preliminary stakeholder conversations described challenges that specialists experience in providing useful advice based upon limited A&G referral information, for example being asked to interpret results of investigations in the absence of relevant clinical history and examination findings. Our public involvement work highlighted an unfamiliarity with the option and use of A&G pathways and a sense of disenfranchisement around the referrals process.

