5.2.7 Definition of the study population

All individuals in the CPRD Aurum database, regardless of age, with a first recorded index tracer condition between 01/01/2015 to 31/12/2022 and 24 months prior registration in CPRD Aurum. We will compare outcomes for patients with a recent history of A&G to those with direct referral, stratified by tracer condition. A&G and direct referrals will be obtained from primary care records in the 24 months prior to index (first diagnosis) date. Patients with both A&G and direct referral will be classified based on whichever happened first. We will include age at index date, gender, neighbourhood deprivation, geographical region, and ethnicity, as common covariates for all analyses as well as covariates (e.g. multiple long term conditions) specific to each tracer condition. There is no comparison or control group.

The tracer conditions will be informed from the work in WP1, including interviews with PCCs, and the experiences and advice of our PPIE and Stakeholder groups.

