5.3 DATA / STATISTICAL ANALYSIS

For WP2a, the outcome for those with an A&G and/or direct referral recorded will be the time to diagnosis from the first recorded A&G or direct referral to index diagnosis date. We will calculate median (interquartile range) days to diagnosis from first recorded A&G or direct referral code and incidence rates per 1,000 person years and present with 95% confidence intervals. We will use flexible parametric survival analysis to compare A&G and direct referral on time to diagnosis. Flexible parametric survival analyses are preferred to Cox proportional hazards regression as they allow easier modelling of time-dependent effects and the ability to determine absolute risks of outcome. Exposure' will be the initial method of referral (A&G, direct referral) prior to index date. Hazard ratios will be presented as unadjusted and adjusted for covariates with 95% confidence intervals (CI).

For WP 2b, individuals with each index condition will be categorised as i) A&G only, ii) direct referral only, iii) A&G and direct referral, iv) no recorded A&G or direct referral in the 24 months before diagnosis:

- negative binomial or zero-inflated negative binomial regression will be used to estimate incidence rate ratios for the number of consultations, referrals and prescriptions in primary care, and number of outpatient appointments,
- robust Poisson regression will be used to compare A&E and unplanned admission in secondary care;
- flexible parametric survival analysis will estimate hazard ratios for mortality.

Rates or ratios will be presented as unadjusted and adjusted for covariates with 95% CI.

As part of the Study Within A Project (SWAP) (see Section 8), the impact of multimorbidity and frailty on decision to use A&G and its outcomes will be considered by including multimorbidity and frailty (defined by Charlson comorbidity index/number of prescriptions and electronic frailty index) as predictors and moderators of A&G outcome in the models.

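### The WP2 common covariate list leaves out calendar time, so growth in A&G use alone can push the WP2a hazard ratio above 1

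*Protocol*

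**What the plan says.** Section 5.2.7 defines the cohort as people "with a first recorded index tracer condition between 01/01/2015 to 31/12/2022 and 24 months prior registration in CPRD Aurum". Exposure is found by looking back: "A&G and direct referrals will be obtained from primary care records in the 24 months prior to index (first diagnosis) date". Section 5.3 makes the WP2a outcome the "time to diagnosis from the first recorded A&G or direct referral to index diagnosis date", compares A&G with direct referral by flexible parametric survival analysis, and promises unadjusted and covariate-adjusted hazard ratios.

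The adjustment set is stated, not deferred: "We will include age at index date, gender, neighbourhood deprivation, geographical region, and ethnicity, as common covariates for all analyses". The same sentence leaves room for further covariates chosen tracer by tracer, and its only example is multimorbidity. Section 5.3 adds multimorbidity and frailty. No WP2 model contains referral date, calendar year or a pandemic period. Section 5.3.1 on confounding promises only to acknowledge unmeasured factors such as severity. Sections 5.3.2 and 5.3.3 treat better recording over time as a limitation to discuss.

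Elsewhere the protocol recognises that time matters. Section 1.2: "The COVID pandemic accelerated use of the A&G process, which has been in use since 2012". Section 1.1.2 says secondary care waiting lists grew after the pandemic. For WP1a, section 4.3 plans joinpoint and segmented regression for the effect of COVID and policy changes on A&G use.

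**The concern.** By the protocol's own account, both the exposure and access to specialist care shifted inside the 2015–2022 window. Two things follow if the model ignores date.

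1. **Look-back selection.** Everyone enters on their diagnosis date. For a given diagnosis date, a longer interval means an earlier referral, when A&G was less common. Long intervals are therefore under-represented among A&G patients, and the A&G hazard ratio rises above 1. This needs no change in waiting times.
2. **Pandemic slowing.** If diagnosis slowed from 2020, the group with more recent referrals carries more of the delay. This pulls the hazard ratio down.

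The listed covariates do not carry referral date, so adjusting for them removes neither. At stake is an adjusted hazard ratio, reported to commissioners and policy makers, that suggests A&G shortens time to diagnosis when it does not, or that hides a real delay.

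**Working it through.** **The plan's own figure.** Inputs from section 5.2.5: 7,000 diagnoses a year × 20% coverage × 8 years = 11,200 (the protocol says about 11,000); 5% with A&G; hazard ratio 1.15; 90% power; 5% significance, taken as two-sided. Schoenfeld: (1.960 + 1.282)² / (0.05 × 0.95 × (ln 1.15)²) ≈ 11,325 events. Power is 89.2% at 11,000 and 89.7% at 11,200. The figure reproduces and is not in dispute. The SE of the log hazard ratio is 1/√(11,000 × 0.05 × 0.95) = 0.044.

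**Growth implied by the protocol.** Section 1.2 gives about 135,000 A&G referrals in February 2023: 135,000 × 12 × 20% = 324,000 a year. Section 5.2.3 gives 1.7 million requests over 2015–2023, or 1.7 million / 9 = 189,000 a year. The ratio is 1.7. Exponential 5-fold growth over nine years would give a similar ratio: mean level (5 − 1)/ln 5 = 2.49 times the start, February 2023 level 5^0.9 = 4.26 times the start, and 4.26/2.49 = 1.71. This is only a rough guide. It compares a national e-RS count with CPRD-coded requests, and it is volume, not the A&G share for any tracer.

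**Mechanism in closed form.** Assume exponential time to diagnosis with rate λ and an A&G share growing at rate g a year. Looking back from diagnosis weights A&G intervals by exp(−g·t), so their rate becomes λ + g. With a 90-day median, λ = 0.693/(90/365.25) = 2.81 a year. A 5-fold rise over 9.5 years gives g = ln 5/9.5 = 0.169. The ratio is (2.81 + 0.169)/2.81 = 1.06. For longer delays the 24-month cut-off makes the average ratio smaller than this simple formula gives.

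**Simulation with true hazard ratio 1.** The protocol's sampling was used: diagnosis in 2015–2022, first referral up to 24 months earlier, all subjects cases. Assumed: A&G share averaging about 5%, growth over 9.5 years, exponential delay, and hazard of diagnosis from March 2020 cut by 0 to 30%. The listed covariates were not simulated. Fitted hazard ratios without a calendar term:

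| Median delay | 5-fold, no slowing | 5-fold, 30% slowing | 20-fold, no slowing | 20-fold, 30% slowing |
|---|---|---|---|---|
| 90 days | 1.060 | 1.014 | 1.119 | 1.033 |
| 180 days | 1.084 | 1.064 | 1.165 | 1.115 |
| 365 days | 1.096 | 1.075 | 1.191 | 1.143 |

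- No growth: 0.99–1.01. A 50-fold rise: 1.05–1.24.
- A separate run with medians of 180 and 270 days and slowing up to 40% gave 1.04–1.09 (5-fold) and 1.08–1.17 (20-fold). Setting aside the 90-day corner, about 1.05–1.10 and 1.08–1.18 are fair summaries.
- Stratified by quarter of first referral: 0.99–1.01 in every scenario.
- Stratified by year of diagnosis, with growth: 1.06–1.26, so not corrected.
- SE of the log hazard ratio at 11,000 cases: 0.042–0.048 without strata and 0.042–0.049 with referral-quarter strata.

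**Consequence for testing.** At 180 days, 5-fold growth and no slowing, ln 1.084 = 0.081 and 0.081/0.043 = 1.88. The chance of a false significant result is Φ(1.88 − 1.96) ≈ 47% instead of 5%. At 20-fold it is about 94%. With a 90-day median, 5-fold growth and 30% slowing it is about 6%.

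**The case against.** **Size is assumed.** The protocol gives no growth figure for the A&G share, no delay distribution and no slowing factor. Section 4.1 makes the rise relative to direct referral a WP1a question. This stands: the omission is certain, but the magnitude is conditional.

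**WP2 is provisional.** Sections 3 and 5 call the design iterative, section 5.2.1 calls it exploratory, and full model terms often sit in a SAP. This stands in part. But section 5.2.7 states a common list for all analyses, and the only part it leaves open is tracer-specific, which calendar time is not. Exploratory status does not excuse omitting a measured variable from a hazard ratio that will be reported.

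**Calendar adjustment does not repair a diagnosed-only cohort.** True. It removes the growth bias and leaves any other consequence of selecting on the outcome.

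**WP2b.** Section 5.3 has a fourth group without A&G or referral in the look-back. Referral date is undefined for it, so a blanket instruction to add that date to every model cannot be carried out. This stands and shapes the fix. The look-back mechanism also does not apply to outcomes after referral, and no size has been calculated for WP2b.

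**Stronger readings.** A reader might infer that either distortion alone could equal the target effect. The calculations do not support that. The strongest pandemic pull in the tabulated grid and its 50-fold extension is 1.048/1.154 = 0.908 (90 days, 50-fold, 30% slowing). A separate run with 40% slowing gives 1.074/1.200 = 0.895. Neither reaches 1/1.15 = 0.870. A reader might also infer that a steep rise is documented; section 1.2 says only that use accelerated.

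**Conclusion.** The point holds for WP2a. The stated covariate list omits calendar time, and with this sampling any growth in the A&G share biases the hazard ratio upward under no effect. Pandemic slowing offsets this in part, and almost wholly in the shortest-delay, 5-fold case (1.01).

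On the log scale, 1.05–1.10 is 35% to 68% of the target (0.049/0.140 and 0.095/0.140), and 1.08–1.18 is 55% to 118% (0.077/0.140 and 0.166/0.140). The look-back component alone reaches 1.15 only with growth of about 20-fold or more, and at 20-fold only with the 180- and 365-day delays. All of this rests on the assumed growth, exponential delays and slowing factors; with a flat A&G share there is no bias.

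For WP2b, adjusting for calendar date is sensible because the same period is spanned, but the documents support no statement of size.

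**What to change.** - **WP2a:** in sections 5.2.7 and 5.3, add the calendar date of the first A&G or direct referral to the adjusted model, as quarterly strata or a flexible spline. Say explicitly that it is the referral date, since diagnosis year leaves the bias in place.
- **Secondary analysis:** report the A&G effect separately for referrals before March 2020 and from March 2020 on.
- **WP2b:** adjust for referral date in comparisons among groups i–iii, and for index diagnosis date in any comparison with group iv.

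**Cost:** one variable already in the extract. In the simulations, stratifying by referral quarter raised the SE of the log hazard ratio by no more than about 0.001, so the stated power is essentially kept. Section 5 says WP2 permissions are still to be sought, so the change can go into that application.

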5.2.4 Outcomes to be measured

For WP2a, the outcome for those with an A&G and/or direct referral recorded will be the time to diagnosis from the first recorded A&G or direct referral to index diagnosis date.

For WP2b, outcomes will be guided by our PPIE and Stakeholder groups as well as emerging results from interviews with PCC's. They are likely to include in the 12 months following referral:

- i. Number of consultations recorded in primary care;
- ii. Number of prescriptions recorded in primary care;
- iii. Number of referrals recorded in primary care;
- iv. AE attendance recorded in HES AE
- v. Number of additional outpatient appointment recorded in HES outpatients
- vi. Overnight unplanned hospital admission recorded in HES APC (admitted patient care);
- vii. Mortality recorded in ONS.

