5.3.1 Plan for addressing confounding

This is a descriptive/exploratory and hypothesis generating study. We will acknowledge in dissemination unmeasured factors like symptom or disease severity may confound associations between the covariates and A&G and in referral following an A&G.

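### The WP2b adjusted utilisation models include no measure of prior consultations, referrals, outpatient, A&E or admission use, although the records can supply it

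*Protocol*

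**What the plan says.** Protocol section 5.2.7 names one adjustment set for WP2: "We will include age at index date, gender, neighbourhood deprivation, geographical region, and ethnicity". This set is to serve every analysis. Each tracer condition may bring further covariates of its own, and the example given is multiple long-term conditions. The same section requires "24 months prior registration in CPRD Aurum", counted back from the first diagnosis, and looks for A&G and direct referrals within those 24 months.

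Section 5.2.4 introduces the WP2b outcomes with "They are likely to include in the 12 months following referral". It lists primary care consultations, prescriptions and referrals, A&E attendance, outpatient appointments, unplanned admissions and mortality. Section 5.3 will "estimate incidence rate ratios for the number of consultations, referrals and prescriptions in primary care, and number of outpatient appointments" by negative binomial or zero-inflated negative binomial regression. It uses robust Poisson regression for A&E and unplanned admission. Results are given unadjusted and adjusted, over four groups: (i) A&G only, (ii) direct referral only, (iii) both, (iv) neither in the 24 months before diagnosis.

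Two further places add covariates. Section 5.3 enters multimorbidity and frailty (Charlson index or number of prescriptions, and the electronic frailty index) as predictors and moderators for the Study Within A Project (SWAP). Section 8.2 makes multiple long-term conditions a WP2 covariate.

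On confounding, section 5.3.1 says only that the team will acknowledge that "unmeasured factors like symptom or disease severity may confound associations".

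**The concern.** In WP2b the clinician chooses the pathway and the outcome is how much care the patient then uses. Earlier use of the same kind is an obvious candidate to predict later use, and it may also bear on the choice of pathway. It is recorded in the same sources as the outcomes, so it is measured confounding, whereas section 5.3.1 speaks only of unmeasured factors. That section repeats the WP1a wording in section 4.3.1. It concerns links between the covariates and A&G, and referral after A&G. It does not address pathway against later utilisation.

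If patients sent down one pathway were already heavier or lighter users, an adjusted ratio that omits prior use carries part of that difference and reads as added or saved workload. Section 1.1.2 cites a survey of 366 GPs in which 78% felt that A&G increased their workload. Section 10.1.2 sends the WP2 associations to policy makers and commissioners. A ratio a few per cent from 1 could therefore be taken as evidence in a live dispute.

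**Working it through.** **The plan's own figure.** The protocol gives no precision or power figure for WP2b. The only WP2 figure (section 5.2.5) is for time to diagnosis: 7,000 × 0.20 × 8 = 11,200, stated as around 11,000. With 5% on A&G and a hazard ratio of 1.15, two-sided power by Schoenfeld's formula is 89.2% for 11,000 and 89.7% for 11,200, against the stated 90%. That figure reproduces and does not depend on this point.

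**What the adjusted model holds for each WP2b utilisation outcome**

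| Outcome | Nearest planned covariate | Prior use of the same kind? |
|---|---|---|
| Consultations | Charlson, frailty, long-term conditions | No |
| Prescriptions | Number of prescriptions, as a multimorbidity measure | In part; time window not stated |
| Referrals | As for consultations | No |
| Outpatient appointments | As for consultations | No |
| A&E attendance | As for consultations | No |
| Unplanned admission | As for consultations | No |

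**Size of the confounding.** The documents give neither the difference in prior use between pathways nor the strength of the link from prior to later use. Both are assumed here. If prior use is higher by a factor 1 + d in one pathway and later use follows prior use with elasticity e, the ratio with no true effect is (1 + d)^e.

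- d = 0.10, e = 0.4: 1.10^0.4 = 1.04
- d = 0.10, e = 0.6: 1.10^0.6 = 1.06
- d = 0.20, e = 0.4: 1.20^0.4 = 1.08
- d = 0.20, e = 0.6: 1.20^0.6 = 1.12

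If the other pathway holds the heavier users, the range inverts to about 0.90-0.96. On another scale, a gap of 0.1 to 0.3 SD in prior use with a log-rate slope of 0.2 to 0.6 per SD gives exp(0.2 × 0.1) = 1.02 to exp(0.6 × 0.3) = 1.20.

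These figures ignore the multimorbidity and frailty terms. If those terms took up half of the effect (again assumed), the first range would shrink to 1.10^0.2 = 1.02 up to 1.20^0.3 = 1.06.

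**Size of the lost precision.** With correlation ρ between prior and later use, adjustment multiplies the residual variance by 1 − ρ². For ρ = 0.3, 0.5 and 0.7 that is 0.91, 0.75 and 0.51, so the standard error falls to 0.95, 0.87 and 0.71 of its value. These are upper bounds on the gain, since the planned proxies already explain some of the variance.

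A negative binomial illustration takes 11,000 patients with 5% on A&G (550 against 10,450), an assumed mean of 10 and an assumed dispersion of 1:

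- Without prior use: SE of the log ratio = √[(1/10 + 1)(1/550 + 1/10,450)] = 0.046, a 95% margin of exp(1.96 × 0.046) = 1.09 either way.
- With prior use explaining a share ρ² of the dispersion: SE = 0.044, 0.040 and 0.034 for ρ = 0.3, 0.5 and 0.7.

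The assumed confounding of 1.04-1.12 is thus of the same order as the sampling margin.

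**Is a pre-referral look-back available?** Registration is guaranteed for 24 months before diagnosis. A patient referred t months before diagnosis therefore has at least 24 − t months before referral: 12 or more if t ≤ 12, 6 if t = 18, none guaranteed if t = 24. Group (iv) has no referral date, so neither the look-back nor the 12-month outcome window is defined for it.

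**The case against.** The strongest reply is that WP2 is unfinished by design. Section 3 says some details await earlier work packages, section 5 says WP2 will be designed iteratively under a separate data application, and section 5.2.1 labels it descriptive and exploratory. The outcomes are only likely ones, and nothing excludes prior use from the open list of tracer-specific covariates. This stands as far as urgency goes. It does not remove the point, because section 5.2.7 already names a common set for all analyses and section 5.3 commits to adjusted ratios. Prior use is not specific to any tracer, so the common set is where it belongs.

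The second reply is that the plan already adjusts for more than demographics. This also stands. Charlson index, number of prescriptions, frailty and long-term conditions are partial proxies for general care use, so the gap is narrower than section 5.2.7 read alone would suggest. They do not record earlier consultations, referrals, outpatient, A&E or admission use.

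A reader might go further and infer that any WP2b ratio could be wholly a product of baseline use, or that a 15% difference in prior use would pass through almost whole, as about 1.15. The documents support neither. They give no baseline difference and no persistence of use. At an elasticity of 0.4-0.6, a 15% difference gives 1.15^0.4 = 1.06 to 1.15^0.6 = 1.09. Full carry-over needs use to be a fixed patient trait, which is a further assumption.

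**Conclusion.** The point holds in a limited form. The adjusted WP2b models contain demographic, tracer-specific, multimorbidity and frailty terms, but no measure of prior consultations, referrals, outpatient appointments, A&E attendances or admissions. The sources that supply the outcomes can supply these counts too. That leaves avoidable confounding and some lost precision.

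The size is conditional. A spurious ratio of about 1.04-1.12 rests on an assumed 10-20% difference and elasticity of 0.4-0.6, before the planned proxies take their share. Its direction is unknown. If pathways do not differ in prior use, the cost is precision only. This is a recommended improvement to a stated method. It does not invalidate WP2b, and it is best made before the WP2 data application is submitted.

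**What to change.** In sections 5.2.7 and 5.3:

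- **Covariate.** For each WP2b utilisation outcome, add to the common covariates the count of the same type in the 12 months before the first A&G or direct referral. Enter it log-transformed (with an offset for zeros) or as a rate over the available look-back. Apply this to the comparison of groups (i) to (iii). End the window before that first date, not at diagnosis, so that use caused by the pathway is not adjusted away.
- **Group (iv).** State an explicit anchor date for both its look-back and its outcome window, or leave it out of this adjusted comparison.
- **Incomplete look-back.** Use a person-time rate, or one registration requirement applied equally to all groups (for example 24 + 12 = 36 months before diagnosis). Avoid a rule that drops patients according to their referral-to-diagnosis interval, because that interval is the WP2a outcome and could select differently by pathway.
- **Data request.** Ask for primary care and HES records that reach back over the look-back period.
- **Confounding text.** Rewrite section 5.3.1 so that it addresses pathway against later utilisation and separates measured from unmeasured factors.

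The cost is one derived variable per outcome. Some patients will have a shorter look-back, or some will be lost under a uniform registration rule. Residual confounding will remain and should still be reported as a limitation.
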